3.1 Study Design

This is an observational cohort study of outpatients with COVID-19. Enrolment will begin in June 2020 and is expected to continue for at least 12 months. Follow-up will be 28 days from enrolment in those who are positive. Those with a negative test will not be followed after enrolment or disclosure of a negative result.

3.2 Study Objectives

The two primary objectives of this observational study are:

Among those who are positive for SARS-CoV-2:

1. Estimate the rate of hospitalization or death during the 28 day follow-up period.
2. Identify risk factors for hospitalization or death.

Other objectives are:

1. Compare characteristics, including demographics, co-morbid conditions or immunosuppression, and other risk factors for disease progression, including hospitalization or death, for the global cohort and by geographic region between those who test positive for the SARS-CoV-2 virus versus those who test negative.
2. Among those who are positive for SARS-CoV-2
 - a. Evaluate health status and the percentage reporting excellent or very good health status during follow-up.
 - b. Determine the percentage reporting a return to pre-morbid health status during follow-up.
 - c. Evaluate change in severity of dyspnoea using a standardized questionnaire²² during follow-up.
3. In a substudy involving selected sites, establish a repository of baseline upper respiratory and blood samples for future studies. These studies will be aimed at molecular characterization of SARS-CoV-2, and the measurement of biomarkers that predict progression of disease. Among participants co-enrolling in INSIGHT 004: Genomics, DNA will be extracted for studies of host genetics to investigate the pathophysiology and host-viral interactions of COVID-19.
4. Use the data collected to inform the design of future randomized intervention studies aimed at reducing the rate of disease progression and morbidity.

3.3 Endpoints

The primary endpoint is hospitalization or death during the 28 day follow-up period. Special facilities are being built for the care of COVID-19 patients requiring medical care. Hospitalization is defined as a stay for at least 18 hours, irrespective of reason, at a hospital or one of these special facilities after study enrolment.

Key secondary outcomes include:

- Participant-reported evaluation of health status
- Change in severity of dyspnoea.

3.4 Sample Size

Sample size is open-ended for this observational study. We estimate that several hundred sites will participate and will enrol approximately 10,000 adults with SARS-CoV-2 infection. Sites in diverse geographic locations on several continents will participate.

For participants with COVID-19, statistical considerations are summarized below. Information on rates of a composite outcome of hospitalization or death for the target

population is scarce, and rates are expected to vary across geographic locations, and possibly over time. Therefore, initial analyses will be descriptive, and sample size estimates will be updated based on the observed event rates, prevalence of risk factors, and newly emerging research questions.

For power calculations, we conservatively assume that 500 out of 10,000 (5%) participants will experience the composite outcome of hospitalization or death by day 28. This is based on the expectation that persons with mild symptoms will be discouraged from seeking SARS-CoV-2 testing at the height of the pandemic, while persons presenting with severe symptoms would not be eligible for this protocol.

Table 1 below summarizes the sizes of the associations of risk factors (dichotomized) with hospitalization or death (odds ratios) that can be detected with 80% and 90% power, using 2-sided tests with significance level of 0.05, assuming 500 or 100 events. For example, with 500 events, an odds ratio of 1.51 can be detected with 80% power for a risk factor with 10% prevalence. For analyses within subgroups, e.g., by age, event numbers may be smaller. With 100 events, an odds ratio of 2.32 can be detected with 80% power for a risk factor with 10% prevalence.

Prevalence of Risk Factor	500 events		100 events	
	80% Power	90% Power	80% Power	90% Power
5%	1.73	1.85	2.99	3.31
10%	1.51	1.59	2.32	2.55
25%	1.34	1.40	1.86	2.02
50%	1.30	1.35	1.76	1.93

Table 1. Odds ratios that can be detected with 80% and 90% power, assuming 500 or 100 persons are hospitalized or die.

For continuous risk factors, odds ratios are expressed per unit increase in the risk factor. Table 2 summarizes the odds ratios per 1 standard deviation higher levels of the risk factor that can be detected with power of 80% or 90% if the association with outcomes is positive (odds ratio > 1) or negative (odds ratio < 1). For example, with 500 events, an odds ratio of 1.17 per 1 standard deviation higher levels of the risk factor can be detected with 90% power. Calculations assume that the risk factor has a normal distribution.

Association	500 events		100 events	
	80% Power	90% Power	80% Power	90% Power
Positive (OR>1)	1.14	1.17	1.33	1.39
Negative (OR<1)	0.88	0.85	0.75	0.72

Table 2. Odds ratios per 1 SD higher levels of a continuous risk factor that can be detected with 80% and 90% power, assuming 500 or 100 events.

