SARS-CoV-2 is a coronavirus that emerged in China in late 2019 causing a novel Corona-Virus Induced Disease (COVID-19). COVID-19 is spreading rapidly throughout the world. While a proportion of people with COVID-19 have sufficiently severe symptoms to require hospitalization at the time of initial symptom onset, in others the disease may remain mild, and in some cases there has been observed a worsening of symptoms a few days after initial presentation with relatively mild symptoms. There is an urgent need for understanding the progression of disease for individuals with SARS-CoV-2 infection/COVID-19 who do not require immediate hospitalization.

This is an international, observational cohort study of adults with SARS-CoV-2 infection/COVID-19 managed as outpatients (not hospitalised). This study will also be a platform for the enrolment of outpatients for randomized trials that will be conducted by the INSIGHT group.

Those with confirmed SARS-CoV-2 infection will form an observational cohort study and be followed for 28 days. Procedures and data collection have been streamlined to facilitate the enrolment of a large number of adults at INSIGHT sites around the world.

The general aim of this study is to estimate the rate of disease progression for adults testing positive for SARS-CoV-2. The primary endpoint for this study and the basis for sample size is hospitalization or death during the 28 day follow-up period. In some locations special facilities are being built/utilized for quarantine/public health reasons for those who are SARS-CoV-2 positive. Hospitalization is defined as a stay for at least 18 hours, irrespective of reason, at a hospital or one of these special facilities after study enrolment.

Secondary outcomes include participant-reported health status and change in severity of dyspnoea.

As the understanding of the natural history of COVID-19 improves based on this and other studies, inclusion criteria and the data collection plan, including the outcomes assessed in this protocol, may be modified.

Study Objectives

The two primary objectives of this observational study are:

Among participants testing positive for SARS-CoV-2:

1. Estimate the rate of hospitalization or death during the 28 day follow-up period.
2. Identify risk factors for hospitalization or death.

Other objectives are:

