1. Compare characteristics, including demographics, co-morbid conditions or immunosuppression, and other risk factors for disease progression, including hospitalization or death, for the global cohort and by geographic region between those who have a positive test for the SARS-CoV-2 virus versus those who have a negative test.
2. Among those positive for SARS-CoV-2:
 - a. Evaluate health status and the percentage reporting excellent or very good health status during follow-up.
 - b. Determine the percentage reporting a return to pre-morbid health status during follow-up.
 - c. Evaluate change in severity of dyspnoea using a standardized questionnaire during follow-up.
3. In a substudy involving selected sites, establish a repository of baseline upper respiratory and blood samples for future studies. These studies will be aimed at molecular characterization of SARS-CoV-2, and the measurement of biomarkers that predict progression of disease. Among participants co-enrolling in INSIGHT 004: Genomics, DNA will be extracted for studies of host genetics to investigate the pathophysiology and host-viral interactions of COVID-19.
4. Use the data collected to inform the design of future randomized intervention studies aimed at reducing the rate of disease progression and morbidity.

Participant Selection

To be eligible for enrolment participants must be ≥ 18 years of age, not be hospitalized (outpatients), and have a signed informed consent. Participants with SARS-CoV-2 infection will be followed for 28 days from enrolment.

Study Plan

Participants who consent for the study and have SARS-CoV-2 infection/COVID-19, will be followed for 28 days in an observational cohort study.

Procedures and data collection have been streamlined to facilitate the enrolment of a large number of adults at INSIGHT sites around the world.

The general aim of this study is to identify risk factors for disease progression, e.g., hospitalization or death. This information will be used to plan and rapidly enrol randomized trials of treatments for COVID-19. Protocols which are developed for the randomized trials by INSIGHT will be separate from this protocol.

2 Background and Rationale

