3.5.1 Inclusion Criteria

- ≥ 18 years of age
- Not hospitalized
- Signed informed consent.

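### Does the eligibility claim in Section 3.4 about severe presenters, which no criterion states, undermine the 5% planning rate or the primary endpoint?

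*Protocol*

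**What the plan says.** The Protocol speaks about severity at entry in three kinds of place.

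- **Planning rationale.** Section 3.4 assumes 500 events in 10,000 participants, calls this conservative, and gives as one reason that "persons presenting with severe symptoms would not be eligible for this protocol".
- **Background.** The opening summary describes a need to understand the disease in people "who do not require immediate hospitalization". It notes that in some cases there has been "a worsening of symptoms a few days after initial presentation with relatively mild symptoms". It describes the cohort as adults managed as outpatients.
- **Eligibility.** The summary states: "To be eligible for enrolment participants must be ≥ 18 years of age, not be hospitalized (outpatients), and have a signed informed consent". Section 3.5.1 repeats this, with care status given as "Not hospitalized". Section 3.5.2 has one exclusion, a known positive test more than 28 days ago.

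Section 3.3 defines hospitalization as "a stay for at least 18 hours, irrespective of reason, at a hospital or one of these special facilities after study enrolment", with no minimum interval after enrolment. The summary gives the general aim in two forms: to "estimate the rate of disease progression for adults testing positive for SARS-CoV-2", and, under Study Plan, "The general aim of this study is to identify risk factors for disease progression, e.g., hospitalization or death". Section 4.1 lists symptoms and dyspnoea severity at enrolment among the risk factors. It plans logistic models at days 7, 14 and 28, Kaplan-Meier and Cox analyses of time to the composite, and analyses by reason for hospitalization.

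**The concern.** Section 3.4 makes a flat statement about eligibility, and the eligibility list does not contain it. The inclusion criterion tests where the person is at consent, not how ill they are or whether admission is imminent. Enrolment is in person and may sit beside a testing station, so someone could consent and be admitted hours later. That person meets every criterion and, if positive and kept at least 18 hours, is a primary event.

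At stake is interpretation. If the 28-day rate is read as later worsening in people who were mildly ill at entry, same-day admissions do not belong in it. Dyspnoea at enrolment might then partly describe an admission already under way rather than predict one. Because the planning rate is low, a small share of participants could be a sizeable share of events.

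**Working it through.** **Inputs from Section 3.4.** N = 10,000; 500 events (5%); two-sided 0.05; detectable odds ratio 1.51 at 80% power for a risk factor with 10% prevalence.

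**Plan's own figure.** Place the 5% at the mean of the risk factor: b = ln 1.51 = 0.412 and a = logit(0.05) − 0.1 × 0.412 = −2.986. This gives p0 = 0.0481 and p1 = 0.0709, with 9,000 unexposed and 1,000 exposed. Take the null variance from the simple average of p0 and p1:

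- null SE = sqrt(0.0595 × 0.9405 × (1/9,000 + 1/1,000)) = 0.00788
- alternative SE = sqrt(0.0481 × 0.9519/9,000 + 0.0709 × 0.9291/1,000) = 0.00842
- z = (0.0228 − 1.96 × 0.00788)/0.00842 = 0.87, so power is 0.81

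The stated 1.51 reproduces. The power arithmetic is not in question.

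**Effect of same-day admissions on the rate.** The documents give no share, so let s be an assumed share, with 5% of the rest having a later event. The total rate is s + (1 − s) × 0.05, a shift of 0.95s.

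- 95% half-width at 5%: 1.96 × sqrt(0.05 × 0.95/10,000) = 0.43 points.
- Break-even: s = 0.427/0.95 = 0.45%, or 45 people. The rate is then 5.43%, and same-day admissions are 0.45/5.43 = 8.3% of events.

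| Assumed s | Total rate | Same-day share of events |
|---|---|---|
| 0.5% | 5.475% | 50/547.5 = 9% |
| 1% | 5.95% | 100/595 = 17% |
| 2% | 6.90% | 200/690 = 29% |

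**Effect on power.** Scaling the log odds ratio by the square root of events, 595 events give exp(0.412 × sqrt(500/595)) = 1.46 in place of 1.51. Extra early events make the planned analysis more powerful.

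**Effect on the dyspnoea odds ratio.** Assume s = 1%, a true odds ratio of 2.0 and 15% dyspnoea prevalence, so that about 25% of later progressors are dyspnoeic. If the same 25% holds among same-day admissions, the exposure odds among cases are unchanged and the odds ratio stays at 2.00. A higher share would raise it and a lower share would reduce it. Nothing in the documents says which applies.

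**Reading the passages together.** The opening summary links symptoms severe enough to need hospitalization with presentation, then defines the cohort as those managed as outpatients. Its eligibility sentence glosses the criterion with the word outpatients, and Section 3.1 uses the same term. On that reading the Section 3.4 clause says that people ill enough to be admitted at presentation are not outpatients and so do not enter. The two summary phrases on mild onset and immediate hospitalization are background; neither sets eligibility. That leaves the person admitted between consent and the end of the same day.

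**The case for a change.** The strongest case for a change is that a sentence about eligibility should match the criteria, that outpatient status is not the same as mild disease, and that the results are meant to inform trials of treatments to reduce progression. A sensitivity analysis setting aside day-of-enrolment admissions would cost little. The event dates are already needed for the Kaplan-Meier and Cox analyses, and removing 10% or 20% of 500 events moves the detectable odds ratio only from 1.51 to exp(0.412 × sqrt(500/450)) = 1.54 or exp(0.412 × sqrt(500/400)) = 1.59.

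The literal mismatch stands, and so does the point that the planned day-28 rate and models pool same-day and later events. The step from there to a required change does not. The Protocol gives hospitalization or death as its own example of progression and counts stays irrespective of reason, so an early admission is an event by definition, not a misclassified one. The Kaplan-Meier curve will show same-day events, and reasons for hospitalization are to be analysed. Setting aside day 0 is itself only a proxy: it discards genuine abrupt worsening on that day and keeps next-day admissions that were equally foreseeable. Whether to add such an analysis is a choice for the Statistical Analysis Plan that Section 4.1 announces. Changing the sentence itself would require ethics approval at each of several hundred sites (Sections 3.4 and 5.2) and would alter no number, result or procedure.

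**Conclusion.** No change to the plan follows. The Section 3.4 clause is a loose paraphrase of the outpatient criterion, used to support a planning figure that the same section calls conservative and says will be updated from observed rates. Any departure from it adds events and so raises power. The 5% rate, Tables 1 and 2 and the primary endpoint stand, and both primary objectives are answered as stated.

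The size of any effect on interpretation is unknown. Below about 45 same-day admissions in 10,000 the shift lies within sampling error. At assumed shares of 0.5% to 2% the total would be 5.5% to 6.9%, still a correct estimate of the endpoint as defined. No distortion of the risk-factor odds ratios has been shown.

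This conclusion rests on reading outpatient as excluding most people already in need of admission, and on the 28-day rate being reported as hospitalization or death from any cause after enrolment, as Section 3.3 defines it. An analyst who wants to report day-of-enrolment admissions separately can do so from dates already needed. If Section 3.4 is opened for other reasons, the clause can be aligned with the criteria at the same time.

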3.5 Participant Selection

This study intends to target enrolment at research sites that can recruit a large number of individuals with SARS-CoV-2. Thus, each participating site will be asked to describe the approach they plan to take for enrolling individuals. Sites may be asked to change their approach to enrolment if the expected percentage positive for SARS-CoV-2 is too low. Enrolment at registered sites may be paused if there are too few positive individuals being enrolled.

The inclusion and exclusion criteria for enrolment are given below.

3.5.1 Inclusion Criteria

- ≥ 18 years of age
- Not hospitalized
- Signed informed consent.

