Data on the relationship between the use of routine medications for chronic conditions and COVID-19 outcomes are limited. It has been hypothesized that since the tissue receptor for SARS-CoV-2 is angiotensin-converting enzyme 2 (ACE2), and higher levels of ACE2 can protect against acute respiratory distress syndrome (ARDS), that the angiotensin receptor blockers and statins upregulate ACE2 and that these might be used to treat COVID-19.²⁰ On the other hand, it has also been suggested that treatment with ACE2-stimulating drugs in people with diabetes and hypertension could increase the risk of developing severe and fatal COVID-19.²¹ One small study has found no association between use of an angiotensin-converting enzyme inhibitor or angiotensin II receptor blocker and risk of death in COVID-19.¹⁰

There is currently little data available in people with COVID-19 who are managed as outpatients. It would be useful to identify risk factors associated with progression of COVID-19 in non-hospitalized individuals leading them to require hospitalization and/or

treatment for COVID-19. This will provide critical information for clinical service planning, and further inform the development of novel therapeutics.

INSIGHT is currently enrolling hospitalized patients with COVID-19 in the INSIGHT FLU 003 Plus observational study. This observational study of outpatients with COVID-19 will complement FLU 003 Plus and address gaps in our knowledge about risk factors for disease progression that lead to hospitalization or death.

Recognizing the critical importance of maintaining front-line clinical services in responding to COVID-19 and protecting health care workers, this study is designed with minimal data collection requirements with careful attention to management of the risks of service diversion and onward disease transmission. To that end, we considered the literature reviewed above and developed a streamlined data collection plan for collection of baseline and follow-up data for adults who test positive for SARS-CoV-2. Throughout this document when referring to testing for SARS-CoV-2, this refers to a test that directly detects SARS-CoV-2 i.e. a nucleic acid test that detect the presence of viral RNA, typically a PCR test, or a viral antigen test, not an antibody test.

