3.5.2 Exclusion Criteria

- Persons with a known positive SARS-CoV-2 test > 28 days ago.

Those who are negative for SARS-CoV-2 at enrolment will not be followed further in the observational cohort. If the test result is indeterminate, re-testing may be carried out according to local standards.

Individuals who have previously been tested

Individuals with a previous positive test for SARS-CoV-2 within 3 days of enrollment may be enrolled without the need for a repeat test at enrollment. If the positive test was > 3 days and < 28 days before enrollment the test will need to be repeated at enrollment.

[figure not shown]

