3.6 Study Plan

The study plan is depicted in Figure 1.

Figure 1: Study plan for participants undergoing SARS-CoV-2 testing and consenting to participation in this observational study.

Footnote

*on the day of enrolment or test done within 3 days before enrolment

¥ includes COVID-19 related out-patient treatments

Enrolment

Outpatient testing for SARS-CoV-2 may be performed in a variety of ways and for a variety of reasons. To avoid risk to health care workers, in many locations, special facilities are being identified for rapid identification of those with COVID-19. We refer to these as “testing stations”. Since the testing stations are likely to be overwhelmed with people seeking testing, we anticipate that separate areas will have to be identified to consent participants for this research study and to collect the required data. We refer to these as “research stations”. Collaborations between the testing and research stations will be important.

For participants who consent to the study, permission to release medical records will be sought and reasons for hospitalization and events during hospitalization will be requested. Information regarding demographics; medical history, including co-morbidities; onset date of symptoms; targeted symptoms, including difficulty breathing; smoking; and targeted medications will be obtained. Contact information for one or two persons who know(s) the participant’s whereabouts will also be recorded.

At the time of enrolment, selected sites participating in a substudy (see Appendix F) will be asked to obtain separate consent for the swabs from the upper respiratory tract and a blood sample sufficient for 4mL of serum to be shipped to a central repository for future respiratory virus research; and 2) co-enrolment in the INSIGHT Genomics Study (INSIGHT 004) where a blood sample sufficient for obtaining 6mL whole blood will be collected and stored. These specimens will be sent to a central repository in the United States for storage.

Proposed research utilizing stored specimens collected per this protocol will be reviewed and approved by the Protocol Team, the INSIGHT Scientific Steering Committee, and NIAID.

Disclosure of SARS-CoV-2 Test Result

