Participants already known SARS-CoV-2 positive within 28 days of enrollment are eligible. If the documented positive test was within 3 days of enrolment they do not need to be retested at enrolment, and will be followed for 28 days. For others being tested at enrolment, results may not be available on the day of enrolment. When the test results become available, participants will be contacted with the test result. If positive for SARS-CoV-2, these participants will be followed for 28 days.

Participants who do not have a positive test result for SARS-CoV-2 at enrolment will not be followed. Repeat testing can be carried out following local guidelines.

Follow-up of SARS-CoV-2 positive participants

During the follow-up period, the status of each participant will be assessed at 7, 14 and 28 days following enrolment. Status may be checked by telephone or by means other than face-to-face visits (e.g., text messages).

Follow-up assessments at 7, 14 and 28 days will include:

- Vital status
- Hospitalization status
- Specific symptoms, including difficulty breathing
- General health status
- COVID-19 related out-patient treatments
- Targeted medications

Participants hospitalized during the 28 day follow-up period may be invited to participate in FLU 003 Plus, if the location of their hospitalization is a FLU 003 Plus site.

[figure not shown]
In summary, there are 4 time points at which data are collected for this observational study:

- 1) enrolment (in person),
- 2) at day 7 (may be by telephone or other means),
- 3) at day 14 (may be by telephone or other means) and
- 4) at day 28 (may be by telephone or other means).

Follow-up will continue through day 28 for all participants regardless of enrolment in other studies or hospitalization prior to day 28.

Figure 2 illustrates how information from the observational cohort study could be used to identify participants for an INSIGHT clinical trial or for FLU 003 Plus.

Figure 2: Study plan for participants in this observational study who may co-enrol in other protocols. Note: participants in this observational study with SARS-CoV-2 infection will be followed for 28 days regardless of participation in other protocols.

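### The eligibility criteria have no look-back for an earlier admission in the same episode, so discharged COVID-19 patients could enter a cohort meant to measure progression from outpatient disease

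*Protocol*

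**What the plan says.** The inclusion criteria in Protocol section 3.5.1 are age 18 or over, signed consent and "Not hospitalized". Section 3.5.2 has one exclusion: "Persons with a known positive SARS-CoV-2 test > 28 days ago". Section 3.6 (Disclosure of SARS-CoV-2 Test Result) adds that "Participants already known SARS-CoV-2 positive within 28 days of enrollment are eligible".

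A re-test rule applies to some of these people. Under section 3.5.2, those with a positive test "within 3 days of enrollment may be enrolled without the need for a repeat test at enrollment". For older results, "If the positive test was > 3 days and < 28 days before enrollment the test will need to be repeated at enrollment". Anyone negative at enrolment is not followed.

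The synopsis describes the population as adults whose infection is managed without hospitalization. Section 2 says it would be useful to "identify risk factors associated with progression of COVID-19 in non-hospitalized individuals leading them to require hospitalization". Section 3.4 defends the assumed 5% event rate partly on the ground that people presenting with severe symptoms will not be eligible. Section 3.3 counts only stays of at least 18 hours that occur after enrolment.

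For baseline data, section 3.6 states: "Information regarding demographics; medical history, including co-morbidities; onset date of symptoms; targeted symptoms, including difficulty breathing; smoking; and targeted medications will be obtained". Appendix B schedules vital and hospitalization status at the follow-up visits and not at enrolment.

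**The concern.** Read as written, the hospital-status criterion describes a person's present state, while the entry window reaches back up to 28 days from a positive test. Someone may be admitted, treated and sent home within that window and then meet every criterion. That person has already had the event the study sets out to predict.

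Both primary objectives are exposed. The 28-day rate would combine first progression with readmission. The risk-factor models would include people selected for whatever led to their first admission. If their later risk also differs from that of never-admitted outpatients, a factor with no effect in either group can show an association in the pooled data. An analysis plan cannot reliably repair this if prior admission was not collected for everyone.

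**Working it through.** **1. Who can enter.** Two cases, checked against sections 3.5.1, 3.5.2 and 3.6:

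- Tested positive on admission 15 days ago, discharged yesterday. Adult, consenting, not in hospital, positive test within 28 days. The test is more than 3 days old and must be repeated. If it is positive again, the person is followed.
- Tested positive in hospital, discharged, and enrolled within 3 days of that test. No repeat test is required, and the person is followed.

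No criterion stops either case. Under section 3.3 the earlier stay is not an event, and a readmission of 18 hours or more is.

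**2. The protocol's own power figure.** Inputs from section 3.4: N = 10,000, 500 events (5%), 10% prevalence, two-sided alpha 0.05, 80% power, stated detectable odds ratio 1.51. I used a Wald test on the log odds ratio with null variance V0 for alpha and alternative variance V1 for power:

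log OR = 1.96 × √V0 + 0.84 × √V1

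- V0 = 1/(1,000 × 0.05 × 0.95) + 1/(9,000 × 0.05 × 0.95) = 0.0234
- V1, with event risks of about 7.0% (exposed) and 4.8% (unexposed), is about 0.0177
- log OR = 1.96 × 0.153 + 0.84 × 0.133 = 0.412, so OR = 1.51

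The stated figure reproduces. The issue is who is in the cohort, and Table 1 is not in question.

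**3. Effect on the 28-day rate.** The protocol gives neither the share s of previously admitted participants nor their readmission risk r. Both are assumptions here. The true rate in never-admitted outpatients is set at the protocol's 5%.

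Pooled rate = (1 − s) × 5% + s × r. With s = 5%:

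| r | Events (9,500 × 5% + 500 × r) | Pooled rate |
|---|---|---|
| 2% | 475 + 10 = 485 | 4.85% |
| 5% | 475 + 25 = 500 | 5.00% |
| 10% | 475 + 50 = 525 | 5.25% |
| 15% | 475 + 75 = 550 | 5.50% |

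For scale, the 95% confidence half-width is 1.96 × √(0.05 × 0.95 / 10,000) = 0.43 points. Only the last row shifts the rate by more than that. Letting s run from 5% to 20% and r from 0 to 15% widens the range to 4.0% (0.80 × 5% + 0) to 7.0% (0.80 × 5% + 0.20 × 15%).

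**4. Effect on a null risk factor.** Assume a factor with 10% prevalence in never-admitted outpatients and a higher prevalence in discharged patients, with no effect in either group. For s = 5%, r = 15% and prevalence 40% in discharged patients:

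- Exposed: 9,500 × 10% + 500 × 40% = 1,150 people; events 950 × 5% + 200 × 15% = 77.5
- Unexposed: 8,850 people; events 8,550 × 5% + 300 × 15% = 472.5
- OR = (77.5/1,072.5) / (472.5/8,377.5) = 1.28; SE of log OR 0.127; z about 1.95; two-sided rejection probability about 50%

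The same formula with other inputs:

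| s | r | Prevalence in discharged | Crude OR | Rejection probability |
|---|---|---|---|---|
| 5% | 2% | 40% | 0.91 | 10% |
| 5% | 5% | 40% | 1.00 | 5% |
| 5% | 10% | 40% | 1.14 | 17% |
| 5% | 15% | 40% | 1.28 | 50% |
| 5% | 15% | 20% | 1.10 | 10% |
| 2% | 15% | 40% | 1.13 | 14% |
| 1% | 15% | 40% | 1.07 | 7% |

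The bias can go either way, and it vanishes when readmission risk equals the outpatient rate.

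**The case against.** The strongest reply is that the protocol's intent is clear. The synopsis describes people managed as outpatients, section 3.4 assumes severe presenters are out, and section 3.6 describes recruitment beside outpatient testing stations. Nothing describes recruiting from discharge lists. The re-test rule also narrows the route considerably. These points stand. They mean that such people could enter; they do not show that they would enter in number. They do not close the gap, because the operative criterion does not carry the intent, and several hundred sites are expected to apply it.

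A reader might go further in four ways that the protocol does not support:

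- *That discharged patients could never be identified afterwards.* Section 3.6 seeks permission to release medical records and section 6.2 allows hospital records to be abstracted. The case report forms are not shown. Some of these people may be found. What can be said is that prior admission is not a named baseline item, so capture would not be systematic.
- *That pressure on sites with low positivity steers them towards discharged patients.* Section 3.5 says only that such sites may be asked to change approach or may be paused. It does not mention known positives or discharged patients.
- *That a null factor would be declared a risk factor half the time.* That is one corner of assumed inputs. Most other settings in the table give 5% to 17%. The odds ratio is also crude, whereas section 4.1 plans models that consider symptoms, dyspnoea, co-morbidities and region.
- *That the power calculation is wrong.* It reproduces.

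The synopsis does allow criteria and data collection to be modified later. That makes the change easy, but does not make it unnecessary.

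**Conclusion.** The point holds as a gap between the stated population and the criteria meant to select it. Followed literally, sections 3.5.1, 3.5.2 and 3.6 can admit people who have already had the endpoint event. Section 3.3 then ignores that event and would count a readmission as first progression.

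The size is unknown. The illustrated shifts, from trivial to larger than the sampling error of the rate, rest entirely on assumed values for the share of discharged patients, their readmission risk and the prevalence of the factor among them. Neither the number affected nor the direction of bias can be read from the protocol, so the error cannot be taken as conservative. Given the low cost of correction, it should be put right.

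**What to change.** Bring section 3.5.1 into line with the synopsis and section 3.4 in one of two ways.

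1. Extend the inclusion criterion so that, besides not being in hospital at enrolment, the participant has had no hospital stay of at least 18 hours for the current SARS-CoV-2 episode before enrolment. The cost is one clause and slightly fewer eligible people.
2. If the sponsor prefers to keep such people, add one enrolment item to section 3.6 and Appendix B: prior hospital stay for this episode, yes or no, with dates. Exclude those who answer yes from the primary 28-day rate and the risk-factor models, and report them separately. The cost is one extra data item in a deliberately streamlined data collection.

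Neither option needs a new procedure.
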